6.1 Statistical and Analytical Issues

6.1.1 Statistical Methods

Statistical analyses will be performed [REDACTED]. All data will be listed, and summary tables and figures will be provided. Table, Figure, and Listing (TFL) mock shells will be provided for all analyses.

Statistical descriptions will be performed by treatment groups. For disposition and demography, description will also be presented overall. Variables recorded for each eye will be described separately for the study eye and for the contralateral eye (if applicable).

[figure not shown]
Baseline is defined as the assessment at randomisation/D1 visit before the first IMD instillation. Missing values at randomisation visit will not be replaced. Change from baseline at any time point is defined as the value at the timepoint minus the baseline value and is calculated only for the post-baseline visits.

For endpoints defined as change from baseline, the descriptive statistics by visit (Screening, D1, D15 and D36) and the change from baseline at D15 and D36 will be presented. For endpoints defined in classes, the descriptive statistics by visit and change from baseline will be presented for the original assessments and in the pre-defined classes.

Disposition, demographics, exposure, history of dry eye, medical/surgical history, will be summarised by treatment group and overall, for the FAS, PP set and SAF set [REDACTED]. Disposition, demographics and history of dry-eye will also be presented for the ITT set. Previous and concomitant ocular/non-ocular treatments will be listed.

Quantitative variables (Continuous data) will be summarised in summary tables indicating the number of non-missing/missing observations (n), mean, standard deviation (SD), median, first quartile (Q1), third quartile (Q3), minimum and maximum.

[figure not shown]
Qualitative variables (Categorical data) will be summarised in summary tables indicating the number of non-missing/missing observations (n), count and percentage of each modality. For all performance and safety analyses, percentages will be calculated based on the non-missing patient count (n) for each column for the patients in the respective analysis set. For all rest analyses, percentages will be calculated based on total patient count (N) for each column for the patients in the respective analysis set (missing counts will be included).

This document is confidential.

Statistical Analysis Plan

Sponsor: Laboratoires Théa; Clinical Investigational Plan No.: LT2769-004

This document is confidential.

SAP text and shells Version: 2.0 07-FEB-2025

Page 13 of 46

Statistical Analysis Plan

Sponsor: Laboratoires Théa; Clinical Investigational Plan No.: LT2769-004

[figure not shown]
6.1.3 Handling of Dropouts and Missing Data

For primary analysis performed on FAS, Mixed Model for Repeated Measures (MMRM) and [REDACTED] method will be applied in case of missing value. [REDACTED] method [REDACTED] assume missing data satisfy the conditions of Missing At Random (MAR). Missing values at randomisation visit will not be imputed.

6.1.4 Determination of Sample Size

The sample size is driven by the statistical hypothesis on the primary objective: to demonstrate the non-inferiority of T2769 compared to Hylo-Forte® in terms of the change from baseline (D1) in total ocular surface staining score assessed on Oxford 0-15 scale, in the study eye at the D36 visit.

This document is confidential.

Statistical Analysis Plan

Sponsor: Laboratoires Théa; Clinical Investigational Plan No.: LT2769-004

6.2 Patient Characteristics

6.2.1 Patient Disposition

Patient disposition will be summarized in tables, by treatment group and overall, for the FAS, ITT, SAF [REDACTED], and PP sets. Moreover, a listing will be provided in all enrolled patients per site and patient.

Information will include:

- Number of patients that met all eligibility criteria
- Number of patients enrolled and patients per analysis set (see section 5)
- Number of patients who completed the clinical investigation
- Number of patients who discontinued the investigation and any primary reason for study discontinuation
- Number of patients per site
- Number of patients attended visits as considered in the analysis

This document is confidential.

Statistical Analysis Plan

Sponsor: Laboratoires Théa; Clinical Investigational Plan No.: LT2769-004

6.2.3 Background and Demographic Characteristics

The demographic and background characteristics to be collected are:

- Age (in years)
- Sex

Similarly to patient disposition, gender, age as continuous and in three classes (<65 / \geq 65 and <85 / \geq 85, as well as age by gender will be summarized in tables, by treatment group and overall, for the FAS, SAF [REDACTED], ITT and PP sets. Moreover, a listing will be provided in ITT per patient for all the demographic data.

6.2.4 Prior and Concomitant Medications and Therapies

Prior medications are medications or non-medicinal therapies that were stopped prior to initiation of the IMD. Concomitant medications are any medications or non-medicinal therapies given concurrently with the IMD, either are ongoing at or began after the initiation of the IMD and before end-of- [REDACTED]

[REDACTED] Prior and concomitant medications will be coded by the Anatomical Therapeutic Chemical (ATC) classification system according to the World Health Organization Drug Dictionary (WHO-DD) version Sep 2024.

[figure not shown]
6.2.5 History of Dry eye

Medical history of dry eye will be collected and summarized separately from the rest of the medical and surgical history.

Dry-eye history will be summarized in table as per collected information in the eCRF, while time from first diagnosis to first IMD intake will also be calculated and summarized in the FAS, PP, ITT and SAF sets [REDACTED].

Variables to be summarised in tables are:

- Localisation (one eye, both eyes)
- Time from diagnosis of dry eye disease (years) [REDACTED]

This document is confidential.

Statistical Analysis Plan

Sponsor: Laboratoires Théa; Clinical Investigational Plan No.: LT2769-004

[REDACTED]

6.2.6 Ocular and Systemic Medical and Surgical History (other than dry eye)

All ocular and systemic medical and surgical history (other than dry eye) will be coded using Medical Dictionary for Regulatory Activities (MedDRA) Version 27.1.

The history will be assumed as ocular or systemic, [REDACTED]. In addition, category will be validated based on the SOC. [REDACTED]

Medical and surgical history will be summarized separately for ocular and systemic history by the number and percent of patients within each SOC and PT in the FAS, PP and SAF sets [REDACTED] [REDACTED]. Conditions that are reported more than once for a given SOC and PT will be counted only once per patient on the PT level for each SOC. Medical and surgical history will be sorted by descending overall frequency, by SOC and PT in the summary table.

All above data will also be listed separately for ocular and systemic history, sorted by patient number, onset date, SOC, and PT in the SAF set.

6.2.7 Treatment Exposure and Compliance

Exposure and compliance as described in the eCRF will be assessed by summarising the below, separately for Hydrabak® (run-in period) and IMDs (active treatment period), by treatment group, for the FAS, PP set, and SAF set [REDACTED]:

- Treated eye (One / Both)
- Treatment duration (in days) for the whole time period for both Hydrabak® and IMDs
- Treatment duration (in days) per period (from D1 to D15 and from D16 to D36) for IMDs only
- Mean Daily Dose Regimen (per day with intake) for the whole time period
- Mean Daily Dose Regimen (per day with intake) per period (from D1 to D15 and from D16 to D36)
- Number of days without treatment intake
- Overall compliance (%)

[REDACTED]

[REDACTED]

This document is confidential.

Statistical Analysis Plan

Sponsor: Laboratoires Théa; Clinical Investigational Plan No.: LT2769-004

6.3 Statistical Analysis

6.3.1 Primary Performance Analysis

The primary performance endpoint is the change from baseline (D1) in total ocular surface staining grade according to Oxford 0-15 grading scheme at D36 in the study eye.

will be performed following original Oxford scale

he primary analysis

The inferential analyses of the primary performance endpoint will aim to assess the non-inferiority of T2769 to Hylo-Forte®. The non-inferiority will be primarily tested using a MMRM approach.

The model will include treatment and scheduled visit time points (D15 and D36) as fixed factors, patient as random factor, and baseline total ocular surface staining (Oxford score) as continuous covariate. Treatment by scheduled visit time point and baseline total ocular surface staining (Oxford score) by scheduled visit time point will be included as an interaction term in the model.

Descriptive tables will also be produced presenting data for total ocular surface staining values and change from baseline at each visit to support the MMRM analysis tables.

The mean and associated SD of the Oxford score on the study eye for each treatment will be graphically displayed by analysis visit for the FAS.

[figure not shown]
This document is confidential.

Statistical Analysis Plan

Sponsor: Laboratoires Théa; Clinical Investigational Plan No.: LT2769-004

Primary performance endpoint will be primarily analysed on the FAS. [REDACTED]

[figure not shown]
[REDACTED]

This document is confidential.

Statistical Analysis Plan

[figure not shown]
Sponsor: Laboratoires Théa; Clinical Investigational Plan No.: LT2769-004

This document is confidential.

Statistical Analysis Plan

[figure not shown]
Sponsor: Laboratoires Théa; Clinical Investigational Plan No.: LT2769-004

This document is confidential.

Statistical Analysis Plan

[figure not shown]
Sponsor: Laboratoires Théa; Clinical Investigational Plan No.: LT2769-004

This document is confidential.

Statistical Analysis Plan

Sponsor: Laboratoires Théa; Clinical Investigational Plan No.: LT2769-004

This document is confidential.

[figure not shown]
Statistical Analysis Plan

Sponsor: Laboratoires Théa; Clinical Investigational Plan No.: LT2769-004

This document is confidential.

Statistical Analysis Plan

[figure not shown]
Sponsor: Laboratoires Théa; Clinical Investigational Plan No.: LT2769-004

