6.1.2 Description of the Measures to be Taken to Minimize or Avoid Bias

6.1.2.1 Randomisation

The use of randomisation attempts to mitigate accidental bias (such as selection bias), promoting comparability of the study groups and serves as a basis for statistical inference for quantitative evaluation of the treatment effect.

The randomisation code list stratified by site and lists of IMDs kit numbers for the packaging is generated by the CRO responsible for biometry. Patients will be randomised on a 1:1 basis to T2769 or Hylo-Forte® respectively.

Randomisation list(s) and lists of IMD numbers for the packaging are to be kept securely by the editor according to their procedures.

The IMD packaging list is to be kept by the company responsible for manufacturing and labelling of the treatment kits.

The randomisation and the IMD kit number will be allocated to the patients according to randomisation list using an Interactive Response Technology (IRT).

Randomisation will occur at Randomisation Visit (Visit #2 - D1) after all procedures have been performed and eligibility for the clinical investigation confirmed. The patient who meets the eligibility criteria will be randomly assigned to treatment and associated to a randomisation number.

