7.2.1 Performance Analyses

Primary [REDACTED] performance endpoint will be primarily analysed on the FAS. Sensitivity analysis of the primary [REDACTED] performance endpoint will be performed on the PP.

The detailed analysis methods for primary and each secondary performance variables will be discussed further in the SAP.

[figure not shown]
Primary performance endpoint

[figure not shown]
The primary performance endpoint is the change from baseline (D1) in total ocular surface staining grade according to Oxford 0-15 grading scheme at D36 in the study eye. The analysis will be performed following original Oxford scale [REDACTED]

The inferential analyses of the primary performance endpoint will aim to assess the non-inferiority of T2769 to Hylo-Forte®. The hypothesis of non-inferiority will be tested by calculating the bilateral 95% CI around the difference between groups (T2769 – Hylo-Forte®) in mean change from baseline in the total ocular surface staining (Oxford score) to D36 in the study eye. If the upper bound is no higher than +2 points, it will be concluded that the null hypothesis can be rejected and that the performance of T2769 is non-inferior to that of Hylo-Forte®.

The non-inferiority will be primarily tested using a Mixed Model for Repeated Measures (MMRM) approach. The model will include treatment and scheduled visit time points (D15 and D36) as fixed factors, patient as random factor, and baseline total ocular surface staining (Oxford score) as continuous covariate Treatment by scheduled visit time point and baseline total ocular surface staining (Oxford score) by scheduled visit time point will be included as an interaction term in the model.

Descriptive tables will also be produced presenting data for total ocular surface staining values and change from baseline at each visit.

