7.10 MANAGEMENT OF POTENTIAL CONFOUNDING FACTORS

[figure not shown]
Baseline value will be included in all MMRM models (if applicable) as covariate.

Other covariates will be explored and detailed in the SAP.

[figure not shown]

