7.15 PROCEDURES FOR REPORTING ANY DEVIATION(S) FROM THE ORIGINAL STATISTICAL PLAN

Any changes from the planned analyses will be described and justified in the SAP and the final CIR.

7.17 DEFINE A STRATEGY FOR POOLING DATA, IF APPLICABLE.

NA.

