9 APPROVAL OF THE CLINICAL INVESTIGATION AND AMENDMENTS

Prior to starting the clinical investigation, the CIP and other relevant documents will be submitted and approved by the IEC/IRB and/or CAs, in accordance with regional/local regulatory requirements. The Sponsor must ensure that all ethical and legal requirements have been met before the first patient is enrolled in the clinical investigation.

Full compliance with this CIP must be sought. To alter the CIP, amendments must be written, approved by the appropriate personnel, and by IEC/IRB/CAs prior to implementation.

All amendments will be distributed to all CIP recipients, with appropriate instructions.

By signing the CIP, the investigator confirms that he/she agrees to perform the clinical investigation as outlined in the CIP.

The CIP is the binding document for the investigator, the Sponsor and its designee; modifications are only valid if agreed upon by the Sponsor and its designee. Modifications must be documented in a signed amended CIP.

The Sponsor will promptly report the following for review or information to the Ethics Committee(s) and the CA for:

- Substantial CIP modifications
- Administrative changes
- Deviations to the CIP implemented to eliminate immediate hazards to the trial patients
- New information that may affect adversely the safety of the patients or the conduct of the clinical investigation. The IEC and the CA must be informed and approve all CIP amendments, in accordance with local legal requirements before implementation. Amendments must be evaluated to determine whether formal approval must be sought and whether the informed consent document should also be revised.

The written signed approval of the CIP amendment must contain specific identification of the document (e.g., the investigator's name and the CIP title and number).

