SAF	Safety Set
SAP	Statistical Analysis Plan
SD	Standard Deviation
[REDACTED]	[REDACTED]
SOC	System Organ Class
SOP	Standard Operating Procedure
STEAE	Serious Treatment Emergent Adverse Event
[REDACTED]	[REDACTED]
TEAE	Treatment Emergent Adverse Event
TFL	Table, Figure, and Listing
WHO	World Health Organization
[REDACTED]	[REDACTED]

This document is confidential.

2. Introduction

This SAP is based on Clinical Investigation Plan (CIP) No. LT2769-004, Version 2.0 dated 09 APR 2024 and the electronic Case Report Form (eCRF) Version 1.0 dated 12 AUG 2024. The analyses follow the guidelines from the International Organization for Standardization (ISO) described in [ISO 14155:2020 Clinical investigation of medical devices for human subjects – Good clinical practice](#)**Error! Reference source not found.**

The SAP will be finalized prior to database lock. Any deviations from the SAP after database lock will be documented in the final Clinical Investigation Report (CIR).

The purpose of this SAP is to ensure that the data listings, summary tables and figures which will be produced, as well as the statistical methodologies that will be used, are complete and appropriate as per study design and objectives.

3. Study Objectives and Endpoints

The aim of this investigation is the comparison of T2769 with Hylo-Forte®.

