6.4 Interim Analysis

Not applicable. No interim analysis is planned for this investigation.

This document is confidential.

Statistical Analysis Plan

Sponsor: Laboratoires Théa; Clinical Investigational Plan No.: LT2769-004

This document is confidential.

SAP text and shells Version: 2.0 07-FEB-2025

Page 28 of 46

Statistical Analysis Plan

Sponsor: Laboratoires Théa; Clinical Investigational Plan No.: LT2769-004

7. Tables, Figures and Listings

[figure not shown]
Mock tables, listings, and figures will be provided in an external document that accompanies this SAP.

This document is confidential.

Statistical Analysis Plan

Sponsor: Laboratoires Théa; Clinical Investigational Plan No.: LT2769-004

[figure not shown]
This document is confidential.

SAP text and shells Version: 2.0 07-FEB-2025

Page 30 of 46

Statistical Analysis Plan

Sponsor: Laboratoires Théa; Clinical Investigational Plan No.: LT2769-004

This document is confidential.

[figure not shown]
Statistical Analysis Plan

Sponsor: Laboratoires Théa; Clinical Investigational Plan No.: LT2769-004

This document is confidential.

Statistical Analysis Plan

[figure not shown]
Sponsor: Laboratoires Théa; Clinical Investigational Plan No.: LT2769-004

This document is confidential.

Statistical Analysis Plan

[figure not shown]
Sponsor: Laboratoires Théa; Clinical Investigational Plan No.: LT2769-004

This document is confidential.

Statistical Analysis Plan

Sponsor: Laboratoires Théa; Clinical Investigational Plan No.: LT2769-004

[figure not shown]
This document is confidential.

SAP text and shells Version: 2.0 07-FEB-2025

Page 35 of 46

Statistical Analysis Plan

Sponsor: Laboratoires Théa; Clinical Investigational Plan No.: LT2769-004

[figure not shown]

This document is confidential.

[figure not shown]
SAP text and shells Version: 2.0 07-FEB-2025

Page 36 of 46

[figure not shown]
11. Deviations of the SAP from the CIP

[figure not shown]
[REDACTED] deviations from the CIP are the following:

- In the CIP it was stated that the summary tables would include the 95% CI for the mean/median (continuous variables) and the 95% CI of the percentages (categorical variables). However, this was removed from the SAP as it was found to not add any extra value while was increasing the complexity of the outputs.

- For Adverse event reporting, more summary tables and details on listings to be provided are outlined in the SAP section 6.3.4.1 in comparison with the CIP.

Statistical Analysis Plan

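### Randomisation is stratified by site but the primary MMRM has no site term: a possible gain in precision is forgone, with no harm to validity

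*SAP*

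**What the plan says.** Protocol 6.1.2.1 describes the list: "The randomisation code list stratified by site", with 1:1 allocation. The visible text gives no block size. About 4 sites are planned (6.1.8), with 74 patients randomised to give 68 evaluable, 34 per group (6.3.8).

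The primary analysis is the same in protocol 7.2.1 and SAP 6.3.1: "The model will include treatment and scheduled visit time points (D15 and D36) as fixed factors, patient as random factor". Baseline Oxford score is a continuous covariate, and treatment-by-visit and baseline-by-visit complete the model. Site is not among the terms. The decision rule in protocol 7.2.1 is: "If the upper bound is no higher than +2 points, it will be concluded that the null hypothesis can be rejected".

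On further covariates, protocol 7.10 says: "Other covariates will be explored and detailed in the SAP". In the visible SAP, site appears only as a count in patient disposition (6.2.1). SAP 6.1.2 (Bias and Confounding) is listed in the contents but its text is withheld, as are parts of 6.3.1 and of section 11.

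**The concern.** A factor used to stratify allocation normally belongs in the analysis model. When arms are balanced within site, site differences largely drop out of the treatment contrast. A model without site still leaves those differences in the residual variance, so the reported standard error can exceed the true one.

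A site effect is plausible here. The endpoint is a graded slit-lamp score, one masked investigator grades all of a patient's visits (protocol 6.1.5.1), and protocol 6.1.1 expects several investigators to bring a range of clinical judgement. The decision rests on one CI bound against +2 with 34 patients per group, so unnecessary width could cost a non-inferiority conclusion that the data would otherwise support.

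**Working it through.** **Inputs from the documents.** Margin 2; two-sided 95% CI; 34 per group; about 4 sites; allocation stratified by site; model terms as above.

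**Assumptions (not in the visible text).** Baseline-adjusted SD, site share of adjusted variance, block size 4, complete data, D15–D36 correlation 0.6, true difference 0 for power.

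**The plan's own figure.** The SD and power behind 34 per group are not visible, so the sample size can only be back-solved. Normal approximation: SD = 2 / [(1.960 + z) × √(2/34)]. With z = 1.282 (90% power), 2 / (3.242 × 0.2425) = 2.54. With z = 0.842 (80%), 2 / (2.802 × 0.2425) = 2.94. The noncentral t gives 2.51 and 2.90, so SDs of 2.5 and 2.9 are used. Half-width at SD 2.5 with no site effect: 1.997 × 2.5 × 0.2425 = 1.21 points.

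**Expected width ratio, without site / with site.** Let s be the site share of adjusted variance, with arms balanced within site.

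- Fixed site effects: 1/√(1 − s) = 1.026, 1.054, 1.118 for s = 5, 10, 20%.
- Site effects drawn at random for 4 sites, where about three quarters of the site variance is realised within a trial: √[(1 − 0.25s)/(1 − s)] = 1.020, 1.041, 1.090.

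**Simulation of the stated model** with and without a site main effect (4 sites of 17, 60,000 trials per scenario). Ranges run from random to fixed, equally spaced site effects. Gaps are from unrounded values.

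| Site share | Width ratio | Power without → with site, SD 2.5 | Forgone, SD 2.5 (points) | Forgone, SD 2.9 (points) | One-sided error without site, SD 2.5 |
|---|---|---|---|---|---|
| 0% | 0.998 | 89.9 → 89.7 | −0.2 | −0.2 | 2.4% |
| 5% | 1.018–1.025 | 90.8 → 91.4; 90.5 → 91.3 | 0.6–0.8 | 1.0–1.4 | 2.2% |
| 10% | 1.040–1.054 | 91.5 → 92.7; 90.8 → 92.5 | 1.1–1.7 | 2.0–2.9 | 2.0–2.1% |
| 20% | 1.089–1.120 | 92.8 → 95.1; 92.2 → 95.2 | 2.3–3.1 | 4.5–5.9 | 1.5–1.8% |

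The simulation agrees with the formulas. With site in the model, the one-sided error is 2.4 to 2.6%. At a 20% share and SD 2.5, the mean half-width falls from 1.181 to 1.084 (random) or from 1.215 to 1.085 (fixed), that is by 0.10 to 0.13 points. Adding site breaks even at a share of about 0.4 to 0.5%. Unequal sites (32/18/12/6) give +1.5 to +2.4%, +3.4 to +5.2% and +7.8 to +11.8% at 5, 10 and 20%.

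**Three checks on what drives these figures.**

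1. *Constant grader offset.* Suppose site adds the same amount at D1, D15 and D36, with raw-score share s and within-site baseline correlation ρ. The ratio is then about √{(1 − r²)/[(1 − s)(1 − ρ²)]}, with r = s + (1 − s)ρ. For s = 20% and ρ = 0.3, r = 0.44 and the ratio is √(0.8064/0.728) = 1.052. Simulation over shares of 5 to 20% and ρ of 0.7 to 0.3 gives 0.1 to 5.1% of width, 0.001 to 0.06 points of half-width and 0 to 1.8 points of power.
2. *Site effects that differ by visit.* The table assumes the same site effect at D15 and D36. With independent effects, a site main effect alone gives ratios of only 1.018 and 1.041 at 10 and 20% (random site effects). Adding site-by-visit restores 1.038 and 1.088.
3. *No balance within site.* Under simple allocation at SD 2.94, the one-sided error without site was 2.3 to 2.9% over ten scenarios of 6,000 trials. The average was 2.5% and the simulation SE per scenario √(0.025 × 0.975/6000) = 0.2 points. The conservatism disappears and only the precision loss remains.

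**The case against.** The case for leaving the model alone is fairly strong. A CI that is too wide errs on the cautious side of the +2 rule. Under the assumed SD of 2.5, power without site is already 89.9 to 92.8%. The site share, SD and block size are all assumed. The mechanism the documents best support is a stable grader and slit lamp per patient. Change from baseline with baseline as covariate absorbs much of that, leaving at most about 5% of width in the first check. The larger gains need sites to differ in response after baseline adjustment, which nothing visible shows. All of this stands and limits the size of the point.

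A reader might infer that the omission is unexplained. The documents do not support that. Protocol 7.10 sends covariates to the SAP, and SAP 6.1.2 and parts of 6.3.1 are withheld, so a reason or a site-adjusted supportive analysis may exist there. A reader might also infer that the CI is necessarily conservative. That needs balance within site, and the visible text gives no blocking.

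It may also be said that the change is not merely administrative, since protocol 7.2.1 states the model in full. Protocol 7.15 says: "Any changes from the planned analyses will be described and justified in the SAP and the final CIR". But protocol section 9 says: "To alter the CIP, amendments must be written, approved by the appropriate personnel, and by IEC/IRB/CAs prior to implementation". The first does not clearly waive the second, so whether an amendment is needed remains open.

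What remains is that the stated primary model leaves out the one factor the visible text names for stratification, and including it costs almost nothing.

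**Conclusion.** The point holds as a low-severity efficiency improvement, limited to the stated primary model. If site predicts the D36 change after baseline adjustment, the CI is wider than it needs to be. Under SD 2.5, four equal sites, blocks of 4, complete data and shares of 0 to 20%, the excess is about 0 to 12% of width (0 to 0.13 points of half-width, against a margin of 2) and about 0 to 3 points of power. At SD 2.9 it is up to about 6 points of power. The true share is unknown and may be close to zero.

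Two stronger readings should be resisted. One is that leaving out site undermines the non-inferiority conclusion. In the stratified scenarios the one-sided error without site stays below 2.5%, and without within-site balance it stays near 2.5%. The other is that the trial is underpowered as a result. The planned power and SD are not visible, and omitting site lowers no power figure that the documents state.

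**What to change.** Before database lock and unblinding, add site as a fixed factor, with a site-by-visit term to match the model's other visit interactions, to the primary MMRM in SAP 6.3.1 and to the PP sensitivity analysis. Pool very small sites by a rule that uses site size only, with the cut-off fixed before unblinding, for example at the blind data review meeting (protocol section 10). Record the change and its justification in SAP section 11, "Deviations of the SAP from the CIP", and in the CIR, and check whether protocol section 9 also requires an amendment. If withheld SAP text already deals with site, confirm that it covers the primary model. If the sponsor prefers to keep site out, a stated reason in the SAP is enough.

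The cost is about 3 degrees of freedom per visit and, if site explains nothing, about 0.2% of CI width and 0.2 points of power. No new data are needed. Timing is the main constraint. SAP section 2 says: "The SAP will be finalized prior to database lock", but version 2.0 is dated 07-FEB-2025 and completion was planned for April 2025, so a further SAP version before lock would be required. If the data are already unblinded, report the site-adjusted model as supportive only.

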6.3.8 Number of Patients Required to be Randomised in the Clinical Investigation

It is planned to randomise 74 patients in order to have 68 evaluable patients (34 per group) for the FAS analysis.

Evaluable patients will be defined as randomised patients having received at least one dose of IMD and with at least one performance endpoint post-randomisation visit.

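### Unless redacted text already does so, the primary model should set an unstructured D15/D36 covariance in place of the random patient factor, which read literally lets the D15 variance move the D36 bound tested against +2

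*SAP*

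**What the plan says.** CIP 7.2.1 describes the primary analysis as an MMRM: "The model will include treatment and scheduled visit time points (D15 and D36) as fixed factors, patient as random factor". Baseline Oxford score is a continuous covariate, and treatment and baseline each interact with visit. SAP 6.3.1 gives the same model, with "patient as random factor, and baseline total ocular surface staining (Oxford score) as continuous covariate". Neither visible text names a residual covariance structure or a degrees-of-freedom method.

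The decision rule is in CIP 7.2.1. It uses the two-sided 95% interval for the D36 difference (T2769 minus Hylo-Forte) in mean change: "If the upper bound is no higher than +2 points, it will be concluded that the null hypothesis can be rejected".

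On sample size, CIP 6.3.8 says: "It is planned to randomise 74 patients in order to have 68 evaluable patients (34 per group) for the FAS analysis". The SD and power behind that figure are not visible.

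CIP 7.2.1 also says: "The detailed analysis methods for primary and each secondary performance variables will be discussed further in the SAP". The public SAP is redacted or cut around the model in 6.1 and 6.3.1.

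**The concern.** Non-inferiority rests on one number, the upper bound for the D36 difference, so its standard error should reflect how much the D36 change varies. A random patient intercept with a single residual variance is compound symmetry, which forces the same variance at both visits. If the true variances differ, the D36 bound borrows from D15 and the one-sided error moves away from 2.5%.

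The direction depends on which visit varies more. A larger D36 variance makes non-inferiority too easy to declare; a smaller one makes it too hard and costs power. A programmer who follows the visible words would fit this model.

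**Working it through.** **Inputs from the documents.** Two post-baseline visits (D15, D36); treatment and baseline both crossed with visit; two-sided 95% interval; margin +2; 1:1 allocation; 34 evaluable per group. The planned loss is (74 − 68)/74 = 8.1%. The 34 per group cannot be reproduced, because SD and power are not visible.

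**Assumed inputs, not in the documents.** D36 residual SD 2.5, within-patient correlation 0.6, complete data, and D15/D36 SD ratio r from 0.7 to 1.2. With SD 2.5 and 34 per group, a plain t-test at zero true difference has 90.2% power.

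**Step 1: the estimate.** Each visit has its own intercept, treatment effect and baseline slope. With complete data, the D36 treatment estimate is therefore the D36 ANCOVA estimate under either covariance structure.

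**Step 2: the standard error.** Residual df per visit are 68 − 3 = 65.
- Unstructured: variance s36², 65 df, critical t 1.997.
- Compound symmetry: variance (s15² + s36²)/2, Satterthwaite df = 2 × 65/(1 + ρ²). With equal variances and ρ = 0.6 this is 130/1.36 = 95.6, critical t about 1.985.

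The ratio of the second standard error to the first is √((r² + 1)/2).

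**Step 3: check of the identity.** Both models were fitted by REML to one simulated complete data set. The unstructured variances were 2.150 (D15) and 4.846 (D36), mean 3.498; the random-intercept total variance was also 3.498. The estimate was 0.8023 in both fits, with SE 0.482 (random intercept) against 0.567 (unstructured).

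**Step 4: consequence.** With the D36 variance alone, the half-width is roughly 1.997 × 2.5 × √(2/34) = 1.21, or 1.216 on average once chance baseline imbalance is included. Non-inferiority is then declared up to an observed difference of 2 − 1.216 = 0.784. Under compound symmetry (400,000 simulated trials per row; the last column is 1 − Φ(1.96 × SE ratio)):

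| r = SD15/SD36 | SE ratio | Half-width | Largest passing difference | One-sided error at true +2 | Normal approximation |
|---|---|---|---|---|---|
| 0.7 | 0.863 | 1.044 | 0.956 | 4.6% | 4.5% |
| 0.8 | 0.906 | 1.095 | 0.905 | 3.8% | 3.8% |
| 0.9 | 0.951 | 1.151 | 0.849 | 3.1% | 3.1% |
| 1.0 | 1.000 | 1.210 | 0.790 | 2.5% | 2.5% |
| 1.1 | 1.051 | 1.272 | 0.728 | 2.0% | 2.0% |
| 1.2 | 1.105 | 1.336 | 0.664 | 1.6% | 1.5% |

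Using the D36 variance alone, the simulated error stays between 2.46% and 2.54% in every row. At r = 1.2, power at zero difference is 85.9% under compound symmetry against 89.7%. With D36 SD 2.0 or 3.0 the errors hardly change: 4.5% at r = 0.7 and 1.5% to 1.6% at r = 1.2.

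**Step 5: dropout.** With 8% of D36 values missing (400 simulated trials per case, correlation 0.5), the averaging is only approximate: for SDs of 1.67 at D15 and 2.5 at D36, the total variance is 4.46 against a mean of 4.55. The direction holds. In that case the mean random-intercept SE is 0.532, while the estimate actually varies with SD 0.633. With the SDs reversed it is 0.543 against 0.445.

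**The case against.** The strongest objection is that the visible text does not establish the fault. SAP 6.3.1 is plainly cut around the model; even the +2 rule is not visible there. CIP 7.2.1 sends the detail to this SAP, so a covariance statement may sit in hidden text. The averaged variance also needs homogeneous residuals, which no visible passage states. The label MMRM often implies a residual covariance, and the patient term may be loose wording for the subject of that covariance. All of this stands, and it makes the point conditional.

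A second objection is size. At ratios of 0.9 to 1.1 the bound moves by about 0.06 points (1.216 − 1.151 = 0.065; 1.272 − 1.216 = 0.056) against a margin of 2. An error of 4.6% needs a D36 variance about twice that of D15 (1/0.7² = 2.04). The documents give no reason to expect that. This stands too.

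A third is that CIP 6.3.8 counts a patient as evaluable with one post-randomisation endpoint, so 34 per group need not all have D36 data. The table is therefore an idealised case.

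What survives is that the term as written, followed literally, makes a D36 claim depend on the D15 variance, and that the remedy costs almost nothing.

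**Conclusion.** This is a cheap improvement, conditional on the redacted text. It holds if the model is programmed as a random intercept with homogeneous residuals and the D15 and D36 variances differ. It has no effect if the variances are equal. If hidden text already sets an unstructured covariance, it falls away, except that a random patient term beside an unstructured 2×2 matrix is redundant.

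The figures rest on assumed SDs, correlation and ratios. They show how sensitive the bound is and do not predict this trial's error rate.

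A reader might infer three stronger claims that the documents do not support:
- The plan never specifies a covariance. The redactions prevent that conclusion.
- The non-inferiority test is anti-conservative. With no SD by visit visible, it could equally be conservative.
- The treatment estimate is biased. With complete data it is the same under both structures; only its standard error differs.

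**What to change.** First check whether the unredacted SAP already sets the covariance. If not, before database lock and unmasking, replace the random patient factor in SAP 6.3.1 with an unstructured within-patient covariance for D15 and D36, estimated by REML, with a stated small-sample degrees-of-freedom method such as Kenward-Roger. Do not keep a separate random patient term beside it.

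If this changes the CIP model, and does not merely spell out what was meant, add it to SAP section 11, where "deviations from the CIP are the following", and to the final report. CIP 7.15 requires this: "Any changes from the planned analyses will be described and justified in the SAP and the final CIR". Part of the section 11 lead-in is redacted, so check that no such entry exists already.

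The cost is a wording change, about one line of code and one extra covariance parameter (three instead of two). If the variances are in fact equal, the half-width is about 1.216 instead of 1.210 (1.216/1.210 = 1.005, or 0.5% wider). Power at zero difference is then 89.65% instead of 89.95%, under the assumed SD of 2.5. Convergence should not be a difficulty with two visits: none of 400 simulated unstructured fits failed with 6 of 68 D36 values missing.
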